12.2.1 Multiplicity strategy for primary and key secondary endpoints

In order to describe the nature of the benefits of olaparib maintenance treatment, PFS, PFS2, TFST, TSST, change from baseline in TOI score and OS will be tested at a 2-sided significance level of 5%.

In addition to these planned analyses, which will be performed and reported in the CSR, in order to strongly control the type I error at 2.5% 1-sided for key label claims, a multiple testing procedure (MTP) will also be employed across the primary endpoint (PFS) and key secondary endpoints (PFS2 and OS). There is no requirement to adjust for multiplicity due to PFS interim analyses, since there are no planned interim PFS analyses with the opportunity to make an early claim of efficacy.

A hierarchical testing strategy will be employed where PFS is tested first using the full test mass (full test mass = α) and key secondary endpoints of PFS2 and OS will then be tested using a MTP with a recycling strategy (i.e., the MTP will recycle the test mass to the endpoint not yet rejected in the hierarchy outlined in Figure 6). The MTP is detailed below.

Figure 6 Multiple Testing Procedure

PFS2 will only be tested (with the test mass split between interim and final PFS2 analyses) if statistical significance is shown for PFS. OS will only be tested if the null hypothesis (of no difference) is rejected for PFS2.

PFS2 will be tested at the time of the primary analyses of PFS and again when there are approximately 60% deaths. OS will be tested at the time of the primary analysis of PFS, again after approximately 206 events (approximately 53% maturity of the 391 patients randomised) and then again when there are approximately 60% deaths (~235 events out of 391 patients randomised). A proportion of alpha will be spent at this first analyses time point for both endpoints to control for multiple testing however different spending functions will be applied for each.

An interim analysis for PFS2 will be performed at the time of the PFS analysis (approximately 180 PFS2 events expected at this time). Statistical significance will be declared at the interim analysis for PFS2 if the 1-sided $p < 0.0125$. Assuming 180 PFS2 events, a $HR \leq 0.70$ would equate to a 1-sided p-value < 0.0125 .

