If the null hypothesis for PFS2 is not rejected at this first analyses time point then PFS2 will be tested again when the final analysis of OS occurs. The type I error will be controlled at 2.5% 1-sided by assigning approximately 1.8% significance level (1-sided) to the final analysis of PFS2 (final significance level to be determined accounting for correlation between the interim and final PFS2 analyses) (Stone 2010). Assuming 300 PFS2 events, a $HR \leq 0.77$ would equate to a 1-sided p-value < 0.018 . If PFS2 is significant at either the interim or final analyses, the full test mass (alpha) will be carried forward to OS.

The first interim analysis for OS will be performed at the time of the PFS analysis (approximately 100 OS events). Statistical significance will be declared at the first interim analysis for OS if the null hypothesis for PFS2 is rejected at the PFS analysis and the observed p-value for OS is $p < 0.0001$.

In addition, a descriptive OS analysis will be performed at the clinically important timepoint of 7 years post the LSR as part of global enrolment (DCO March 2022). An administrative alpha spend of 0.0001 will be assigned to account for this analysis. The descriptive interim OS analysis 7 years after the LSR is proposed as a clinically relevant timepoint since most events of disease recurrence and subsequently ovarian cancer deaths occur 5-10 years after diagnosis after which death rates approach that of women in the general population (Harter P et al 2010, Tewari K et al 2019).

The second interim analysis for OS will be performed when approximately 206 OS events have occurred (~53% maturity of the 391 patients who were randomised in SOLO1). The final OS analysis will be performed at approximately 60% maturity (~235 events/391 patients who were randomised in SOLO1).

The significance level will be controlled at the 5% level (2-sided) by subtracting the alpha spend at the first interim analysis for OS (0.0001) and the administrative alpha spend at the descriptive OS analysis 7 years post last subject randomised (0.0001) from the overall 5% alpha (i.e., $0.05 - 0.0001 - 0.0001 = 0.0498$) and then assigning the remaining alpha to the second interim OS analysis timepoint (206 OS events; approximately 53% maturity) and the final OS analysis timepoint (235 OS events; approximately 60% maturity) using the Lan De Mets O'Brien-

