12.2.3 Analysis of secondary endpoints

12.2.3.1 Analysis of PFS2 endpoint

An initial PFS2 analysis will be performed at the same time as the primary analysis of PFS and will use the same methodology and model. A further analysis of PFS2 will be performed when the OS data are approximately 60% mature.

As a sensitivity, the analysis of PFS2 will be repeated in those patients whose gBRCAm status is confirmed by the central Myriad test. A KM plot of PFS2 in this subset of patients will be presented by treatment group.

The sensitivity analysis outlined for 12.2.2.1 will not be repeated for PFS2 with the exception of a Kaplan-Meier plot of the time to censoring where the censoring indicator of the primary PFS2 is reversed.

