PFS2 analysis will be performed using the same methodology and model as PFS. If PFS2 is not statistically significant at the primary PFS analysis, then a further analysis of PFS2 will be performed when the OS data are approximately 60% mature. If PFS2 is statistically significant at the primary PFS analysis, then no further analysis of PFS2 will be performed unless requested by a regulatory authority. The type of progression (objective progression by RECIST, progression by CA-125, symptomatic progression or other) will also be summarised by treatment arm.

As a key sensitivity, the analysis of PFS2 will be repeated in those patients whose gBRCAm status is confirmed by Myriad centrally. A KM plot of PFS2 in this subset of patients will be presented by treatment group. This sensitivity analysis will also be repeated excluding any patients who did not have a tBRCA mutation status confirmed by Foundation Medicine. The sensitivity analysis outlined for PFS in Section 4.2.2 will not be repeated for PFS2 with the exception of a KM plot of the time to censoring where the censoring indicator of the primary PFS2 is reversed (what was originally a censored event in the primary PFS2 analysis becomes an actual event and what originally was a PFS2 event becomes a censored event).

In addition, a sensitivity analysis of PFS2 using the marginal model approach of Wei, Lin and Weissfeld (Wei LJ et al 1989) will be undertaken where patient risks will be partitioned from randomisation to PFS and from PFS to PFS2.

Time from second progression to previous assessment will be summarised by treatment arm.

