6 CHANGES OF ANALYSIS FROM PROTOCOL

All efficacy and HRQoL will be analysed using FAS.

Section 3.2.1 Progression free survival

Added clarification that according to the RECIST 1.1 guidelines an overall visit response of PD also requires an absolute increase of > 5 mm in the sum of the diameters of the target lesions.

Section 3.2.7 Time to earliest progression by RECIST or CA-125 or death Derivations will be relative to randomization (CSP states start of study treatment). Also, censoring will use the earliest of the last evaluable RECIST assessment or the last available CA-125 measurement (CSP states most recent).

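### SAP 4.2.3 drops the later PFS2 analysis after a significant interim, although the protocol makes only the second formal test conditional, and the change is not declared

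*SAP*

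**What the plan says.** **Protocol, analysis of PFS2.** Section 12.2.3.1 plans an initial analysis alongside primary PFS and then states: "A further analysis of PFS2 will be performed when the OS data are approximately 60% mature". The synopsis says the same. Neither attaches a condition.

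**Protocol, testing of PFS2.** Section 12.2.1 first gives the timing without condition: "PFS2 will be tested at the time of the primary analyses of PFS and again when there are approximately 60% deaths". It then limits the second formal test: "If the null hypothesis for PFS2 is not rejected at this first analyses time point then PFS2 will be tested again". SAP 4.2.1 carries both statements in nearly the same words.

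**SAP, analysis of PFS2.** Section 4.2.3 goes further. Once PFS2 has reached significance at the interim, "no further analysis of PFS2 will be performed unless requested by a regulatory authority".

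**SAP, declared changes.** Section 6 lists three items: the analysis set ("All efficacy and HRQoL will be analysed using FAS"), the absolute-increase clarification for target-lesion progression, and the derivation and censoring of the RECIST or CA-125 endpoint. PFS2 is not among them.

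**The concern.** A test and an estimate are different things. Once PFS2 has been rejected there is no reason to test it again, and the multiple testing procedure says so. It does not follow that the mature estimate should be dropped. Protocol 12.2.1 keeps the two apart: it describes the planned analyses to be reported in the study report, and then introduces the testing procedure as an addition, "in order to strongly control the type I error at 2.5% 1-sided for key label claims".

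If the interim crossed and nobody asks for more, the published PFS2 result is the early one, selected because it crossed. Estimates selected that way lean towards larger effects. The final OS result would be reported without PFS2 at the same cut-off. The sponsor itself expects OS to be confounded by later PARP inhibitor use, mainly in placebo patients (protocol 1.3.1 and 12.3), so a matched PFS2 estimate would help readers interpret OS.

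The treatment of PFS2 also stands out among the post-progression endpoints. SAP 4.2.5 and 4.2.6 repeat TFST, TSST and TDT at every planned OS analysis without condition, although TDT is labelled supportive. Protocol 3.1 and 6.2.6 keep patients under 12-weekly assessment for second progression, so the data will exist.

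**Working it through.** **Inputs**
- Interim: "approximately 180 PFS2 events expected at this time" (protocol 12.2.1), with a one-sided level of 0.0125 and a stated HR threshold of 0.70.
- Final: 300 PFS2 events, one-sided level about 1.8%, stated HR threshold 0.77 (protocol 12.2.1).
- Allocation 2:1; 391 patients randomised.

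**Reproducing the plan's figures**

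SE(log HR) = 1/√(D × 2/3 × 1/3) = 1/√(2D/9). Critical HR = exp(−z × SE).
- 180 events: SE = 1/√40 = 0.158; critical HR = exp(−2.241 × 0.158) = 0.70. Agrees.
- 300 events: SE = 1/√66.7 = 0.122; critical HR = exp(−2.097 × 0.122) = 0.77. Agrees.
- Final level: with correlation √(180/300) = 0.775, interim level 0.0125 and total 0.025, the final one-sided level solves to 0.0180. Agrees with 1.8%.

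**Precision lost if the later analysis is dropped**

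The ratio of interval widths on the log scale is √(180/300) = 0.775, so the mature interval is about 23% narrower. Equivalently, the interim interval is about 29% wider (1/0.775 = 1.29). For an illustrative observed HR of 0.70:

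| Analysis | Events (share of 391) | 95% CI |
|---|---|---|
| Interim | 180 (46%) | 0.51 to 0.95 |
| Final | 300 (77%) | 0.55 to 0.89 |

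The event counts are planning assumptions. The primary analysis is triggered at about 196 PFS events, so 180 PFS2 events by then looks high. With 120 at the interim the ratio is √(120/300) = 0.632, or 37% narrower. A smaller final count works the other way: 180 against 235 (the planned number of deaths) gives √(180/235) = 0.875, or about 12% narrower.

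**Selection effect**

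The documents give no assumed true HR for PFS2, so a range is shown. With μ = log(true HR), c = log(critical HR) and a = (c − μ)/SE, the mean log HR among trials that cross is μ − SE × φ(a)/Φ(a).

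| Assumed true HR | Interim events | Mean reported HR if crossed (geometric) |
|---|---|---|
| 0.70 | 180 | 0.62 |
| 0.60 | 180 | 0.57 |
| 0.50 | 180 | 0.50 |
| 0.70 | 120 | 0.57 |

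For example, at a true HR of 0.70 and 180 events: a = (−0.354 + 0.357)/0.158 ≈ 0.01; φ/Φ ≈ 0.79; −0.357 − 0.158 × 0.79 = −0.481; exp(−0.481) = 0.62. The overstatement is material for a moderate effect and negligible for a large one.

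**The case against.** The best defence is that the protocol is itself mixed. Section 12.2.1 already stops formal testing after an interim rejection, and SAP 4.2.3 can be read as carrying that through. The primary endpoint follows the same pattern: PFS is analysed once, and again only if health authorities ask (protocol 12.2.2, SAP 4). Related mature evidence is planned in any case, because TSST is repeated at each OS analysis with its HR, interval and Kaplan-Meier plot. SAP 4.2.3 also leaves regulators a route to an update.

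Much of this stands. A reader might infer that the SAP reverses one clear, unconditional commitment. The documents do not support that, because the conditional test is in the protocol too. A reader might also infer damage to error control or to PFS2's role as gatekeeper for OS. There is none: rejection at the interim passes the full alpha to OS, and a second look at PFS2 would change nothing. Nor would final OS stand without any mature post-progression evidence, since TSST covers part of that ground.

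What does not stand is the step from test to analysis. Protocol 12.2.3.1 and the synopsis promise an analysis, and protocol 12.2.1 conditions only the test. The parallel with PFS is weak because the protocol states the single-analysis rule for PFS openly, whereas for PFS2 it states the opposite. TSST depends on when treatment starts and does not replace investigator-recorded second progression.

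**Conclusion.** The point holds as an undeclared narrowing of a planned analysis, with an inconsistency inside the SAP: the timing sentence in 4.2.1 against the rule in 4.2.3. It is a descriptive loss and does not threaten the inference.

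The loss depends on two things: a significant interim, and no regulatory request. The documents do not report the interim PFS2 result, so a reader should not conclude that the mature estimate will be missing. If the interim did not cross, SAP 4.2.3 itself requires the later analysis.

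If both conditions are met, the mature log-scale interval forgone would be about 23% narrower. This assumes 180 and 300 events, 2:1 allocation and the usual large-sample variance. The figure is illustrative, since SAP 4.2.1 states neither event count. Any overstatement in the early estimate depends on the unknown true effect.

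**What to change.** Replace the conditional sentences in SAP 4.2.3 with wording such as:

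> *PFS2 will be re-analysed at the final OS analysis in all cases (HR, 95% CI and Kaplan-Meier plot). If PFS2 was significant at the interim, this analysis is descriptive and carries no alpha.*

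Align the timing sentence in SAP 4.2.1, so that the second formal test is conditional on non-rejection and the second analysis is not.

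Listing the deviation in Section 6 instead would document the change but would not restore the estimate, so it is not sufficient alone.

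The cost is one extra run of existing outputs on data already being collected. Patient follow-up and the testing procedure do not change.

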4.2.4 Overall survival (OS)

OS data will be analysed at the time of the primary analysis of PFS and will use the same methodology and model (provided there are sufficient events available for a meaningful analysis [≥20 deaths], if not descriptive summaries will be provided). A further interim analysis of OS will be performed when ~206 events are observed (approximately 53% maturity of the 391 patients randomised) and a final analysis of OS will be performed when the OS data are approximately 60% mature (~235/391 patients randomised).

An additional descriptive analysis for OS will also be performed at 7 years post the last patient randomised as part of global enrolment (DCO March 2022).

As a key sensitivity, the analysis of OS will be repeated in those patients whose gBRCAm status is confirmed by Myriad centrally. A KM plot of OS in this subset of patients will be presented by treatment group. This sensitivity analysis will also be repeated excluding any patients who did not have a tBRCA mutation status confirmed by Foundation Medicine.

The remaining sensitivity analyses outlined for PFS in Section 4.2.2 will not be repeated for OS with the exception of a KM plot of the time to censoring where the censoring indicator of the primary OS is reversed (what was originally a censored event in the primary PFS2 analysis becomes an actual event and what originally was a PFS2 event becomes a censored event).

A summary of survival status at the time of analysis will be produced. This will summarise the number of patients who have died, who are still in survival follow-up, who are lost to follow-up or who have withdrawn consent.

In addition, duration of follow-up will be summarised using medians:

- In censored (not died) patients only: Time from randomisation to date of censoring (date last known to be alive)
- In all patients: Time from randomisation to the date of death or to the date of censoring for censored patients.

At the time of the last analysis of OS, the subgroup analyses and global interaction test detailed for PFS in Section 4.2.2 will be repeated for OS.

Exploratory analyses of OS

Exploratory analyses of OS adjusting for impact of subsequent PARP inhibitor trial or treatment may be performed if a sufficient proportion of patients switch. The decision to adjust and final choice of methods will be based on a blinded review of the data and the plausibility of the underlying assumptions. Baseline and time-dependent characteristics will

be explored, and summaries of baseline characteristics will be summarised for placebo patients, splitting between those that have and haven't switched at the time of the analyses. This will be performed outside of the CSR.

4.2.5 Time to first subsequent therapy or death (TFST) and time to second subsequent therapy or death (TSST)

Time to first subsequent therapy or death (TFST) and time to second subsequent therapy or death (TSST) will be analysed at the same time as the primary analysis of PFS and using the same methodology and model. The HRs for the treatment effect together with 95% CIs will be presented. KM plots will be presented by treatment arm. In addition, the number of patients who received further therapy relative to progression (before, after, no progression) will also be presented by treatment arm.

Summary tables of first and second subsequent therapies by treatment arm will be provided, as well as response to first and second subsequent therapy by treatment arm.

Further analyses of these endpoints will be performed at the time of each planned analysis of OS data.

As a key sensitivity, the analyses of TFST and TSST will be repeated in those patients whose gBRCAm status is confirmed by Myriad centrally. KM plots of TFST and TSST in this subset of patients will be presented by treatment group. These sensitivity analyses will also be repeated excluding any patients who did not have a tBRCA mutation status confirmed by Foundation Medicine.

4.2.6 Time to study treatment discontinuation or death (TDT)

Time to study treatment discontinuation or death (TDT) will be analysed at the same time as the primary analysis of PFS and using the same methodology and model. The HR for the treatment effect together with 95% CIs will be presented. A KM plot will be presented by treatment arm. No multiplicity adjustment will be applied as this is viewed as a supportive endpoint.

Further analyses of these endpoints will be performed at the time of each planned analysis of OS data.

As a key sensitivity, the analyses of TDT will be repeated in those patients whose gBRCAm status is confirmed by Myriad centrally. A KM plot of TDT in this subset of patients will be presented by treatment group. This sensitivity analysis will also be repeated excluding any patients who did not have a tBRCA mutation status confirmed by Foundation Medicine.

4.2.7 Time to earliest progression by RECIST 1.1, CA-125 or death

Time to progression by RECIST 1.1, CA-125 or death will be performed at the same time as the primary analysis of PFS and will use the same methodology and model.

The number (%) of patients reporting a CA-125 progression, and a combined objective progression and/or CA- 125 progression will be tabulated.

No multiplicity adjustment will be applied as this is viewed as a supportive endpoint (to PFS).

4.2.8 Best overall RECIST response (BoR)

For each treatment arm, Best Overall Response (BoR) derived programmatically from investigator data will be summarised by n (%) for each category (CR, PR, SD, NED, PD, NE). No formal statistical analyses are planned.

The ORR and DCR will be summarised (i.e., number of patients (%)) by treatment group, in patients in the FAS (ITT population) with measurable disease at baseline. In addition, for patients who have an objective response, the duration and onset of the response will be summarised.

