3.1.1 Target lesions (TLs)

Measurable disease is defined as having at least one measurable lesion, not previously irradiated, which is ≥ 10 mm in the longest diameter (LD) (except lymph nodes which must have short axis ≥ 15 mm) with CT or MRI and which is suitable for accurate repeated measurements.

A patient can have a maximum of 5 measurable lesions recorded at baseline with a maximum of 2 lesions per organ (representative of all lesions involved suitable for accurate repeated measurement) and these are referred to as target lesions (TLs). If more than one baseline scan is recorded then measurements from the one that is closest to randomisation will be used to define the baseline sum of TLs. It may be the case that, on occasion, the largest target lesion does not lend itself to reproducible measurement in which circumstance the next largest lesion, which can be measured reproducibly, should be selected.

All other lesions (or sites of disease) not recorded as TL should be identified as NTL at baseline. Measurements are not required for these lesions, but their status should be followed at subsequent visits.

Note: For patients who do not have measurable disease at entry (i.e. no TLs) but have non-measurable disease, evaluation of overall visit responses will be based on the overall NTL assessment and the absence/presence of new lesions (see Section 3.1.3 for further details). If a patient does not have measurable disease at baseline then the TL visit response will be not applicable (NA).

For patients with no evidence of disease (NED) at baseline (i.e. no TLs and no NTLs), evaluation of overall visit responses will be based on absence/presence of new lesions. If no TLs and no NTLs are recorded at a visit, both the TL and NTL visit response will be recorded as NA and the overall visit response will be NED.

Table 2 TL Visit Responses

Visit Responses	Description
Complete Response (CR)	Disappearance of all target lesions since baseline. Any pathological lymph nodes selected as target lesions must have a reduction in short axis to <10 mm
Partial Response (PR)	At least a 30% decrease in the sum of diameters of TL, taking as reference the baseline sum of diameters

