3.2 Outcome Variables

At each visit patients will be assigned a RECIST visit response of CR, PR, SD, PD, NED (applies only to those patients entering the study with no evidence of disease at baseline), NE depending on the status of their disease compared to baseline and previous assessments, using programmatically derived overall visit response from Investigator RECIST assessments. This will be repeated using the time point responses and relevant dates from the BICR.

Where applicable, outcome variables will be programmatically derived using data from Investigator RECIST assessments unless otherwise stated.

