3.2.8 Best overall RECIST response (BoR)

Best overall response (BoR) is calculated based on the overall visit responses from each RECIST assessment (Table 4). It is the best response a patient has had following randomisation but prior to starting any subsequent cancer therapy and prior to RECIST progression or the last evaluable assessment in the absence of RECIST progression.

Categorisation of BoR will be based on the RECIST criteria using the following response categories: complete response (CR), partial response (PR), stable disease (SD), No Evidence

of Disease (NED; applies only to those patients entering the study with no disease at baseline), progressive disease (PD) and not evaluable (NE).

Best overall response will be programmatically derived from the investigator data.

For determination of a best response of SD, the earliest of the dates contributing towards a particular overall visit assessment will be used. SD should be recorded at least 12 weeks +/- 1 week, i.e. at least 77 days (to allow for the assessment window), after randomisation. For CR/PR, the initial overall visit assessment which showed a response will use the latest of the dates contributing towards a particular overall visit assessment.

For patients whose progression event is death, BoR will be calculated based on data up until the last evaluable RECIST assessment prior to death.

For patients who die with no evaluable RECIST assessments, if the death occurred \leq 25 weeks (i.e. 24 weeks ± 1 week) after randomisation then BoR will be assigned to the progression (PD) category. For patients who die with no evaluable RECIST assessments, if the death occurred \geq 25 weeks (i.e. 24 weeks ± 1 week) after randomisation then BoR will be assigned to the non-evaluable (NE) category.

Progression events that have been censored due to them being more than two missed visits after the last evaluable assessment will not contribute to the BoR derivation.

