A patient will be classified as a responder if the RECIST criteria for a CR or PR are satisfied at any time prior to RECIST progression or the last evaluable assessment in the absence of RECIST progression, up to the earliest of the defined analysis cut-off point or the start of subsequent therapy. For each treatment group, the objective response rate (ORR) is the number of patients with a CR or PR post-baseline divided by the number of patients in the group in the FAS with measurable disease at baseline. Only patients with measurable disease at enrolment can achieve an objective response of CR or PR.

Duration of response will be defined as the time from the date of first documented response until date of documented progression or death in the absence of disease progression. The end of response should coincide with the date of progression or death from any cause used for the PFS endpoint. The time of the initial response will be defined as the latest of the dates contributing towards the first visit response of PR or CR. If a subject does not progress following a response, then their duration of response will use the PFS censoring time.

Time to onset of objective response is defined as the time from the date of randomisation until the date of first documented response. The date of first documented response should coincide with that used for the RECIST 1.1 BoR endpoint. Time to response will not be defined for those patients who do not have documented response.

The disease control rate (DCR) is defined as the percentage of patients who have at least one confirmed visit response of CR or PR or have demonstrated SD or NED for at least 23 weeks

(i.e. 24 weeks ± 1 week) prior to any evidence of progression. In the case of SD and NED, follow up assessments must have met the SD or NED criteria for a minimum interval of 23 weeks following randomisation.

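### SAP 4.2.8 restricts the disease control rate to patients with measurable disease, so the NED route in its own definition can never contribute

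*SAP*

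**What the plan says.** SAP 3.2.8 defines DCR as a percentage of patients who reach control by one of two routes: "confirmed visit response of CR or PR or have demonstrated SD or NED for at least 23 weeks". It then sets a duration condition for the second route, "In the case of SD and NED, follow up assessments must have met the SD or NED criteria", for a minimum of 23 weeks after randomisation. NED is thus named twice as a way of achieving disease control. Section 3.2.8 states a denominator for ORR but none for DCR.

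SAP 4.2.8 supplies the DCR denominator. A single sentence puts ORR and DCR together and summarises both by treatment group "in patients in the FAS (ITT population) with measurable disease at baseline". The BoR summary earlier in the same section has separate SD and NED categories and carries no such restriction.

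Three places in the SAP say who can be NED:

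- Section 3.2, on visit responses: "NED (applies only to those patients entering the study with no evidence of disease at baseline".
- Section 3.2.8, on best overall response: "applies only to those patients entering the study with no disease at baseline".
- Section 3.1.1, which spells out what the baseline state means: "For patients with no evidence of disease (NED) at baseline (i.e. no TLs and no NTLs".

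Section 3.1.1 also gives the opposite state: "Measurable disease is defined as having at least one measurable lesion, not previously irradiated".

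The protocol does not settle the matter. Its sections 11.1.2.7 and 12.2.3.5 cover BoR and ORR and do not mention DCR. SAP section 6, on changes from the protocol, does not mention it either.

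**The concern.** The definition and the analysis population exclude each other. A measurable-disease denominator suits ORR, because 3.2.8 says that only such patients can have an objective response. It does not suit a rate whose definition gives credit for staying free of disease.

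The mismatch bears on this design in particular. The trial gives maintenance treatment to responders. Protocol 4.1 defines clinical complete response as no measurable or non-measurable disease with a normal CA-125, and protocol 3.1 has such patients followed as NED. They are one of the two levels of the only randomisation stratification factor. Protocol 4.1 also admits partial responders who have no measurable disease but a CA-125 still above normal. The restriction in 4.2.8 drops both kinds of patient from DCR.

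A programmer following 4.2.8 would produce a rate for a subset under a definition written for a broader group. A reader of the table who knows 3.2.8 would assume that sustained NED had been counted.

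**Working it through.** The plan states no DCR figure, so there is none to reproduce. The check is one of definitions.

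**Step 1. Who is in the denominator.** Under 4.2.8, patients with measurable disease at baseline. By 3.1.1 they have at least one measurable lesion. The target lesion (TL) response is NA only where there was no measurable disease at baseline, so for these patients it is never NA.

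**Step 2. How NED arises.** Table 4 assigns NED in one row only: TL response NA, non-target lesion (NTL) response NA, and no new lesions.

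**Step 3. Enumerate Table 4.** Inputs are six TL responses (CR, PR, SD, PD, NE, NA), five NTL responses (CR, non-CR/non-PD, PD, NE, NA) and three new-lesion states (no, NE, yes).

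| Baseline status | Combinations | PD | CR | PR | SD | NE | NED |
|---|---|---|---|---|---|---|---|
| Measurable disease (TL not NA) | 5 × 5 × 3 = 75 | 43 | 4 | 12 | 8 | 8 | **0** |
| Non-measurable only (TL NA, NTL not NA) | 1 × 4 × 3 = 12 | 6 | 2 | 0 | 2 | 2 | **0** |
| No lesions (TL NA, NTL NA) | 1 × 1 × 3 = 3 | 1 | 0 | 0 | 0 | 0 | **1** |

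The first row sums to 43 + 4 + 12 + 8 + 8 = 75 and the second to 6 + 2 + 2 + 2 = 12. In the third row the remaining combination, with new lesions NE, has no entry in Table 4; this does not affect the result. These are counts of table entries, not of patients.

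NED occurs only in the third row, and 4.2.8 excludes every patient in that row. A patient with measurable disease whose lesions all disappear is CR, not NED. The second row shows that patients with non-measurable disease only can reach CR or SD, and they are excluded too.

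**Step 4. Size.** Let *s* be the share of the FAS without measurable disease at baseline, DCR_m the rate in patients with measurable disease and DCR_n the rate in the others. Then

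DCR(full FAS) = (1 − *s*) × DCR_m + *s* × DCR_n,

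so the full-FAS rate differs from the rate as planned by *s* × (DCR_n − DCR_m). The documents give none of these three quantities. For illustration only, with assumed values of *s* and the 391 patients in the FAS:

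| Assumed *s* | Excluded (391 × *s*, rounded) | DCR denominator under 4.2.8 |
|---|---|---|
| 20% | 78 | 391 − 78 = 313 |
| 40% | 156 | 391 − 156 = 235 |
| 60% | 235 | 391 − 235 = 156 |
| 80% | 313 | 391 − 313 = 78 |

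**The case against.** The strongest reply is that little depends on this. DCR is not among the protocol's objectives or outcome variables. It is absent from SAP Table 1, from the table of formal analyses and from the multiple testing procedure in 4.2.1. Section 4.2.8 plans no formal analysis of these summaries. The omitted patients are visible elsewhere: the BoR table by arm includes NED without restriction, PFS covers the whole FAS, and 4.2.2 gives Kaplan-Meier proportions alive and progression free at six-monthly intervals. For a patient who entered with NED, holding that status to 23 weeks is close to being progression free at that time. All of this stands, and it limits the importance of the point.

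It can also be said that the number remains interpretable. Within measurable disease, CR, PR and SD held for 23 weeks are well defined, and the NED term is merely empty. That is fair, but the definition and the denominator still disagree, and the SAP gives no rule for choosing between them. Nor can the restriction be read as applying to ORR alone, because one clause governs both rates.

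A third reply is that a full-FAS DCR is only one way out, since removing NED from the definition also ends the conflict. This stands as well. The full-FAS version follows the definition as written, but the documents do not prove that it was intended.

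**Conclusion.** The inconsistency is real. As written, the NED component of DCR is exactly zero in both arms, and patients with only non-measurable disease are also omitted. This follows from the definitions and needs no assumption about the data. The numerical effect on the rate cannot be computed, because baseline disease status is not reported in the documents; the denominators shown for 20% to 80% rest on assumed shares.

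The consequence is one descriptive percentage that does not match its own definition. PFS, PFS2 and OS are not affected.

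A reader might infer two stronger things:

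- **That the trial fails to describe disease control in its population.** The documents do not support this. They give DCR no such role, and the BoR table and PFS report the omitted patients.
- **That the word *confirmed* in the DCR definition should be deleted because no confirmation rule exists.** The SAP sections on response state none. However, the modified RECIST criteria are in protocol Appendix F, which is not in the available text, so the absence of a rule cannot be established.

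**What to change.** In SAP 4.2.8, keep the measurable-disease denominator for ORR and summarise DCR separately in the full FAS by treatment arm, using the Table 4 overall visit responses. Naming Table 4 matters. Section 3.2.8 reserves objective response for patients with measurable disease, whereas Table 4 gives an overall CR to a patient whose only lesions were non-target and have disappeared. A full-FAS DCR needs to say that such a CR counts.

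If the sponsor did intend a measurable-disease DCR, the alternative is to remove NED from the definition in 3.2.8 and label the rate as applying to that subset.

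Either route costs a phrase or two in the SAP; the first also changes the denominator of one descriptive table. That table may already exist. Protocol 3.1 places the analysis of all efficacy variables at the primary analysis, SAP section 5 shows that the PFS analysis preceded this SAP version, and 4.2.8 schedules no repeat. If a DCR table has been issued, it should be re-issued or footnoted with the population used and a statement that NED could not contribute.
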